### 7.1.2 Endpoints

### 7.1.2.1 Primary Endpoints

Feasibility will be based on multiple radiation planning and treatment parameters. For proton to be deemed feasible, no greater than 10% of patients should experience one of the following events: a) Patient cannot be given treatment because anatomy is such that a dosimetrically satisfactory treatment plan cannot be devised. For example, the dosimetry is unsatisfactory if

<95% of target volume is covered by 95% of the dose, b) Patient receives greater than 50% of their total treatment (for any reason-unable to set patient up within acceptable limits of tolerance, patient unable to tolerate treatment position or immobilization for duration of treatment) with photon beam radiotherapy (using a backup photon plan, c) Patient is unable to complete all of his/her treatments within 10 days of estimated date of treatment completion or requires a treatment break greater than 5 days.

Acute Toxicity is defined as any grade 3 or higher toxicity, considered probably or definitely related to radiation, observed within 90 days from start of therapy, excluding cranial nerve palsies or nerve root symptoms as these may be due to the tumor itself or prior surgery. Toxicities will be graded using the NCI Common Terminology Criteria for Adverse Events (CTCAE) Version 4.0.

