#### 7.1.2.2 Secondary Endpoints

Late toxicity is defined as any grade 3 or higher toxicity, considered probably or definitely related to radiation, observed later than 90 days from completion of therapy excluding cranial nerve palsies or nerve root symptoms as these may be due to the tumor itself or prior surgery. Late toxicities will be graded according to the CTCAE version 4.0. The time frame for late toxicity is open-ended and late toxicities have been known to occur a year or more after therapy. Follow-up for late toxicity will cease when a patient experiences disease progression, since 2nd line therapies may then be initiated.

Progression-free and overall survival are defined as the time from start of radiotherapy to first documented progression (local or distant event for PFS), death due to any cause or last patient contact alive. The local control rate (i.e., local progression only) may also be evaluated.

Fatigue will be scored by the Brief Fatigue Inventory (BFI), a validated instrument, which will be evaluated at the following time points: Pre-radiation, during treatment, at the inspection visit, and at approximately 3, 6, 9, 12 months post-radiation and then every 6 months for years 2 and 3, and yearly for year 4 and 5. It is expected that BFI score will increase (as fatigue worsens) in the first 6-12 months post-radiation and then the BFI score will decrease (as fatigue improves) at 12-24 months post-radiation.

Neurocognitive function will be assessed by the FACT-BR, which will be evaluated at preradiation, during treatment, at 3, 6, 9, 12 months post-radiation and then every 6 months.

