#### **Feasibility**

A feasibility rate  $\geq 90\%$  is considered acceptable. We will assume a beta (5,1) prior, which is information equivalent to feasibility established in 5 of 6 treated patients. If the number of patients in whom proton is deemed feasible is less than or equal to the number in the table below then termination will be considered as it is highly unlikely that the feasibility rate is  $\geq 90\%$ , as noted by the Bayesian posterior probabilities.

D ' D 1	C D '1 '1'	• ,				
Bayesian Rule	for Feasibili	ıty				
Patients treated in each stratum	3	6	9	1		
				2		
Patients in whom proton is	1	4	6	9		
feasible						
Posterior Prob[feasibility rate	0	0	0	0		
>90%]		•	•	•		
	0	0	0	0		
	4	9	4	8		
Action	Т	Terminate enrollment				

Acute toxicity will be divided into 2 categories to best characterize toxicities in this disease. Non-Neurologic Acute Toxicity

Because proton therapy is expected to spare normal tissues, a non-neurologic acute toxicity rate  $\leq 20\%$  is considered acceptable. We will assume a beta (1,5) prior, which is information equivalent to toxicity in of treated patients. If the number of patients with non-neurologic acute toxicity equals or exceeds the number in the table, then termination will be considered as it is likely that the toxicity rate is >10%, as noted by the Bayesian posterior probabilities.

Bayesian Rule for Non-Neurologic Acute Toxicity						
Patients treated	3	6	9	1		
				2		
Patients who experience acute	2	2	3	4		
toxicity						
Posterior Prob[toxicity rate	0	0	0	0		
>20%]			•			
	8	6	7	7		
	0	2	0	6		
Action	Te	Terminate enrollment				

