#### Neurologic Acute Toxicity

Because radiation therapy is directed to the craniospinal axis, a neurologic acute toxicity rate  $\leq 10\%$  is considered acceptable. We will assume a beta (1,5) prior, which is information equivalent to acute neurologic toxicity in one of 6 treated patients. If the number of patients with neurologic acute toxicity equals or exceeds the number in the table, then termination will be considered as it is likely that the toxicity rate is  $\geq 10\%$ , as noted by the Bayesian posterior probabilities.

Bayesian Rule for Neurologic Acute Toxicity					
Patients treated 3 6 9 1					
				2	

Patients who experience acute toxicity	1	1	2	2	
Posterior Prob[toxicity rate	0	0	0	0	
>10%]		7	Q	. 7	
	1	0	4	6	
Action	To	erminate e	nrollment		

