### 7.1.4 Statistical Analyses

Feasibility. The initial target sample size of 12 patients will be revised to 12 additional base of skull patients to be treated with pencil beam protons and evaluated for feasibility by the new definition. It is anticipated that up to 5 additional spine patients may be enrolled. So the total enrollment after this amendment will be up to 17 patients (12 base of skull and 5 spine). The statistical analysis will calculate the posterior probability that the feasibility rate is >90%. This analysis will be conducted 2 ways: based on all 26 patients treated and on all 17 patients treated after the modification. The definition of infeasibility will be that which was current when the patient enrolled on the trial. There will be no retroactive re-grading of infeasibility in the base of skull patients.

Acute Toxicity. All toxicities observed within 90 days from start of therapy will be graded by CTC Version 4.0 and tabulated. Special attention is paid to neurologic toxicity.

Late Toxicity. All toxicities observed later than 90 days from start of therapy will be graded by the CTCAE version 4.0 and tabulated.

Progression-free and overall survival will be estimated by the survival analysis methods. It is most likely that these time-to-event outcomes will be summarized as part of the phase II study.

Fatigue is scored on a 10-point scale based on the Brief Fatigue Inventory Questionnaire. At each time point, the BFI score will be summarized by mean and standard deviation, and plotted over time. We will examine the plots for the expected worsening of function in the 6-12 months post-radiation and gradual improvement from 12-24 months. The fatigue scores will be summarized in detail in the phase II study.

Neurocognitive function (FACT-Br) will be summarized by descriptive statistics and scatter plots. It is most likely that the neurologic outcomes will be summarized as part of the phase II study.

Estimation of Event Rates. The table below displays the 90% exact binomial confidence

intervals based on 12 patients treated.

intervals ous	ed on 12 patients	i catea.			
No. of	%	90%	No. of	%	90%
Events		exact	Events		exact
		CI			CI
0	0.0	17.5*	7	58.3	31.5,
					81.9
1	8.3	.43,	8	66.7	39.1,
		33.9			87.7
2	16.7	3.0,	9	75.0	47.2,
		43.8			92.8
3	25.0	7.2,	10	83.3	56.1,
		52.7			97.0
4	33.3	12.3,	11	91.7	66.1,
		60.9			99.6
5	41.7	18.1,	12	100.0	82.5*
		68.5			

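### The neurologic stopping boundary and the toxicity rates leave out cranial nerve and nerve root events even when they are attributed to radiation; report both with and without them

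*Combined protocol and SAP*

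**What the plan says.** Section 7.1.2.1 limits acute toxicity to grade 3 or higher events "considered probably or definitely related to radiation, observed within 90 days from start of therapy, excluding cranial nerve palsies or nerve root symptoms". The exclusion and its stated reason read in full: "excluding cranial nerve palsies or nerve root symptoms as these may be due to the tumor itself or prior surgery". Section 7.1.2.2 counts late toxicity "later than 90 days from completion of therapy excluding cranial nerve palsies or nerve root symptoms", with the same grade and attribution requirement. Section 7.2.2 takes the phase II endpoints from Section 7.1.2 unchanged.

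In Section 7.1.3 the acute toxicity endpoint "will be divided into 2 categories to best characterize toxicities in this disease", non-neurologic and neurologic. The neurologic part begins "Because radiation therapy is directed to the craniospinal axis, a neurologic acute toxicity rate" of 10% or less is acceptable, and continues "We will assume a beta (1,5) prior, which is information equivalent to acute neurologic toxicity in one of 6 treated patients". Termination is considered at 1 of 3, 1 of 6, 2 of 9 or 2 of 12 patients. No separate definition of neurologic toxicity there, or in Section 7.2.3, brings the excluded events back.

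Section 7.1.4 has all toxicities graded and tabulated and adds: "Special attention is paid to neurologic toxicity". Section 7.2.4 tabulates all acute and late toxicities in phase II and calculates rates with 95% confidence intervals.

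Two other criteria use probable or definite attribution without any nerve exclusion: item (d) of the primary objective in Section 2, and the statement on Grade 4 toxicity in Section 4.6.

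**The concern.** The reason given for the exclusion is possible tumor or surgical cause. The attribution requirement in the same sentence already screens for that. An event put down to tumor or surgery is out before the exclusion is applied, so the only further events it can remove are those judged probably or definitely due to radiation.

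Eligible tumors arise in the skull and spine, where cranial nerves and nerve roots can lie close to the target. Acute toxicity is a primary objective of the feasibility phase. The numerical rule meant to detect neurologic harm therefore takes no account of two classes of radiation-attributed neurologic event, and a toxicity rate computed on the defined endpoint will not include them. Because the boundaries are so small, a single uncounted event can decide a look.

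**Working it through.** **Inputs.** Prior Beta(1,5), acceptable rate 10%, and boundaries 1/3, 1/6, 2/9 and 2/12, all from Section 7.1.3. Two quantities are not in the documents and are assumed: the true rate of radiation-related neurologic toxicity, and the share f of affected patients whose only qualifying event is a cranial nerve palsy or nerve root symptom.

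**Step 1: reproduce the plan's table.** With x events in n patients the posterior is Beta(1+x, 5+n−x), and Prob[rate >0.10] equals P(Bin(5+n, 0.10) ≤ x). For n=12 and x=2: P(Bin(17, 0.10) ≤ 2) = 0.167 + 0.315 + 0.280 = 0.762. All four looks give 0.813, 0.697, 0.842 and 0.762. These agree with the printed posteriors wherever the digits are legible; part of that table row is damaged in the text available to me.

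**Step 2: leave one event out at the boundary.** The same formula with x−1:

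| Patients | Boundary | Posterior, event counted | Posterior, event not counted |
|---|---|---|---|
| 3 | 1 | 0.81 | 0.43 |
| 6 | 1 | 0.70 | 0.31 |
| 9 | 2 | 0.84 | 0.58 |
| 12 | 2 | 0.76 | 0.48 |

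At each look the count moves from the terminate side to the continue side. This step needs no assumption about how common such events are.

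**Step 3: chance of crossing by patient 12.** Let p be the counted rate, p = true rate × (1−f), and q = 1−p. Not crossing requires no event in the first 6 patients and at most one in the next 6 (this also satisfies the look at 9). So

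P(cross) = 1 − q^6 × (q^6 + 6 p q^5).

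True rate 20%, f = 0: q^6 = 0.2621 and 6pq^5 = 0.3932, so P(cross) = 1 − 0.2621 × 0.6554 = 0.83. True rate 20%, f = 50%: p = 0.10, q^6 = 0.5314 and 6pq^5 = 0.3543, so P(cross) = 1 − 0.5314 × 0.8857 = 0.53.

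| Assumed true rate | f = 0 | 10% | 25% | 50% | 75% |
|---|---|---|---|---|---|
| 20% | 0.83 | 0.79 | 0.71 | 0.53 | 0.29 |
| 30% | 0.95 | 0.93 | 0.87 | 0.71 | 0.42 |

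**Step 4: effect on the endpoint rate.** The expected number of counted patients among 50 is 50 × true rate × (1−f). At 20% this is 10, 9, 7.5, 5 and 2.5 for the same five shares.

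**Step 5: consistency across sections.** A Grade 4 cranial nerve palsy judged probably related to radiation makes the subject infeasible under Section 4.6, yet is not an acute toxicity under Section 7.1.2.1. Section 2(d) would count it if unexpected.

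**The case against.** The exclusion is a prespecified choice with a stated reason. Section 1.1 says that compression of adjacent structures causes most clinical symptoms of chordoma. With no comparator, an investigator's judgment that a nerve deficit is probably related to radiation does not reliably remove tumor or surgical causes, so counting these events could push the rate up wrongly. This stands, and it is why deleting the exclusion outright is a debatable trade-off. The 10% limit and the prior were also stated for the endpoint as defined. By the Step 3 formula the rule already crosses with probability 0.29 at a true rate of 5% and 0.53 at 10%, so widening the endpoint would call for recalibration.

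Three stronger readings are tempting, and the documents do not support them.

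- A reader might infer that the trial cannot respond to nerve injury. Other neurologic toxicities still count toward the boundary. Section 4.6 and Section 2(d) carry no nerve exclusion, Section 8.3.2 sends all SAEs to the DSMC regardless of attribution, and Section 8.5 has the Medical Monitor review all AEs with power to recommend suspension or termination. What remains is narrower: Section 4.6 applies to Grade 4 and Section 2(d), as printed, to unexpected toxicity above Grade 3. A Grade 3 nerve event attributed to radiation therefore enters none of these numerical criteria.
- A reader might infer that all reported toxicity is biased low. Sections 7.1.4 and 7.2.4 tabulate all toxicities, so the events remain visible. Only rates computed on the defined endpoints omit them, and uncertain attribution means that the inclusive rate is not simply the correct one.
- A reader might count as harm the fall in crossing from 0.53 to 0.29 at a true rate of 10% with half the events excluded. Section 7.1.3 calls 10% acceptable, so a crossing there is a false alarm and fewer of them is not lost protection.

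Nor do the documents show that these events are frequent within the acute window. Section 8.1 lists no nerve palsy among common acute effects and places its serious neurologic harms among late effects.

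**Conclusion.** The point holds in limited form. As written, the exclusion acts only on events already attributed to radiation; the neurologic boundary does not count them and the defined acute and late rates omit them. That one event at the boundary changes the outcome of a look follows from the plan's own prior and limits. The loss in crossing probability does not: it rests on an assumed true rate and an assumed excluded share, and at 20% it runs from small (0.83 to 0.79 with 10% excluded) to large (0.83 to 0.29 with 75% excluded). The calculation also treats patients as independent and takes the looks as tabulated; crossing means that termination is considered, not that it follows. This is a cheap improvement, not a defect that invalidates the rule.

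**What to change.** Keep the current endpoint and boundaries. Prespecify in Sections 7.1.4 and 7.2.4 that the neurologic posterior, and the acute and late toxicity rates with their confidence intervals, are also computed including cranial nerve and nerve root events that are grade 3 or higher, new or worsened from the pre-treatment assessment, and judged probably or definitely related to radiation. Give both versions to the Medical Monitor and the DSMC at each look. Reconcile Sections 2(d) and 4.6 with Sections 7.1.2.1 and 7.1.2.2 on whether these events count.

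No new data are needed: the Section 6.0 schedule has a pre-treatment history, examination and toxicity assessment, and Section 6.1 has a neurologic evaluation at each follow-up examination. The cost is a little more analysis, some attribution noise, and a somewhat higher rate in the inclusive version.

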#### 7.1.2.2 Secondary Endpoints

Late toxicity is defined as any grade 3 or higher toxicity, considered probably or definitely related to radiation, observed later than 90 days from completion of therapy excluding cranial nerve palsies or nerve root symptoms as these may be due to the tumor itself or prior surgery. Late toxicities will be graded according to the CTCAE version 4.0. The time frame for late toxicity is open-ended and late toxicities have been known to occur a year or more after therapy. Follow-up for late toxicity will cease when a patient experiences disease progression, since 2nd line therapies may then be initiated.

Progression-free and overall survival are defined as the time from start of radiotherapy to first documented progression (local or distant event for PFS), death due to any cause or last patient contact alive. The local control rate (i.e., local progression only) may also be evaluated.

Fatigue will be scored by the Brief Fatigue Inventory (BFI), a validated instrument, which will be evaluated at the following time points: Pre-radiation, during treatment, at the inspection visit, and at approximately 3, 6, 9, 12 months post-radiation and then every 6 months for years 2 and 3, and yearly for year 4 and 5. It is expected that BFI score will increase (as fatigue worsens) in the first 6-12 months post-radiation and then the BFI score will decrease (as fatigue improves) at 12-24 months post-radiation.

Neurocognitive function will be assessed by the FACT-BR, which will be evaluated at preradiation, during treatment, at 3, 6, 9, 12 months post-radiation and then every 6 months.

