### **3.4** Early Withdrawal of Subjects

### 3.4.1 When and How to Withdraw Subjects

- Recurrent or Progressive Disease: Subjects who have clinical or radiologic evidence of recurrent disease will undergo an evaluation to document the nature of the abnormality. If recurrent or progressive cancer is diagnosed, the subject will be considered off study at that time.
- PI Decision: Subjects may be withdrawn at any time during the study if the PI believes it is in the subject's best interest. In this event, the reasons for withdrawal will be documented.
- Subject Participation: Refusal to continue treatment, follow-up, comply with the protocol or withdrawal of consent. In this event, the reasons for withdrawal will be documented.
- Adverse Event (including intercurrent illness, unacceptable toxicity).

Once the subject has discontinued treatment, the primary reason for discontinuing treatment must be clearly documented in the subject's records and on the CRF. The investigator will assess each subject for response at the time of withdrawal.

Every effort will be made to follow all subjects off study for toxicity and survival unless patient withdraws consent. If subjects withdraw from the study at any time, we will ask for his/her written permission to continue to access medical records for overall survival. Acute toxicities will be assessed for 90 days from the first date of treatment. Survival will be followed for a minimum of 5 years.

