#### **4.6** Treatment Duration

Proton radiation therapy will in most instances be completed within 9 weeks of the start of treatment. This may be extended if subjects require a break from treatment. Criteria for break would include any **Grade 3 or 4** toxicity, depending on the clinical situation as determined by the treating physician. All subjects experiencing Grade 4 toxicity considered probably or definitely related to radiation will be considered infeasible in the feasibility phase of the study.

Version: 04/04/2014

Continuation of treatment and/or further treatment plans will be decided at the discretion of their treating physician.

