### 6.1 Post-treatment Evaluation and Follow-up

All subjects will be evaluated weekly during the course of the proton therapy, at the inspection visit (approximately 90 days from treatment start) and approximately every three months from the last dose of treatment either by the treating radiation oncologist or a referring physician for two years, and approximately every 6 months for year 3 and then yearly for years 4 and 5. Patients will be treated and followed for 90 days from the start of radiation treatment to determine feasibility and safety (acute toxicity) for the initial phase of the study before moving to the second phase of the study.

Each follow-up examination will consist of interval history and physical examination, including a neurologic evaluation and toxicity assessment. A Brief Fatigue Inventory and FACT-Br will also be obtained. Assessment of the disease by MRI will be performed at intervals of 3 months for 2 years and then every 6 months for year 3 and annually for years 4 and 5.

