#### 7.2.2 Endpoints. Same as in 7.1.2

Acute Toxicity. Late toxicity. Fatigue & Neurocognitive function. Progression-free and overall survival.

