#### Radiation Toxicities

Radiation side effects are typically divided into those that occur acutely and those that occur later. Common acute radiation side effects include fatigue, skin irritation or erythema, alopecia, nausea, vomiting and diarrhea. Typically, these side effects can be controlled with medication. Late side effects that are unlikely to occur would include radiation necrosis of the brain, brainstem injury, vascular effects (e.g. stroke), severe dementia, blindness, deafness, paralysis, and skin necrosis. Another rare but serious late side effect is the development of second tumors. It is hoped that proton radiation will substantially reduce both acute and late side effects by reducing the amount of normal tissue that is irradiated.

Acute radiation effects, through post treatment day 90 of treatment, and late radiation effects will be evaluated using the CTCAE 4.0..

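### Acute toxicity ends 90 days from the start of therapy but late toxicity begins 90 days from its completion, which leaves a gap; the Phase II late-toxicity rate also has no time point

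*Combined protocol and SAP*

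**What the plan says.** **Acute window.** Section 7.1.2.1 counts Grade 3 or higher related toxicity "observed within 90 days from start of therapy". Section 3.4.1 agrees: "Acute toxicities will be assessed for 90 days from the first date of treatment".

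**Late window.** Section 7.1.2.2 counts the same grade and attribution if "observed later than 90 days from completion of therapy". It leaves the time frame open-ended and stops late-toxicity follow-up at progression.

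**Other wordings.** The feasibility analysis in 7.1.4 uses the other clock: "All toxicities observed later than 90 days from start of therapy will be graded". Section 8.1 (Radiation Toxicities) says "Acute radiation effects, through post treatment day 90 of treatment, and late radiation effects will be evaluated using the CTCAE 4.0", which is unclear about its starting point.

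**Phase II.** The endpoint line reads "7.2.2 Endpoints. Same as in 7.1.2". Section 7.2.1 gives the characterisation of toxicity rates as a purpose of this phase. Section 7.2.4 promises toxicity rates with 95% confidence intervals, quotes a maximum half-width of ±14% on 50 patients, and places acute and late toxicity in an analysis completed within 1 year of the end of accrual. Kaplan-Meier is named for progression-free survival, overall survival and time to local failure, which are analysed 2-3 years after accrual. Section 7.3 expects 4 years of enrolment.

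**The concern.** The two windows should meet, but they run from different clocks. A related severe event can fall after the acute window has closed and resolve before the late window opens, and then neither Phase II endpoint counts it.

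The second issue concerns what the late rate estimates. Patients will have been followed for very different lengths of time when late toxicity is analysed, and some will have stopped contributing at progression. A single rate with no time attached then depends partly on when the data are cut. It is hard to compare with other series, or to use in designing later trials, which 7.2.4 gives as an aim for its estimates of clinical outcomes.

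**Working it through.** **1. Length of the gap.** The acute window ends at day 90 from start. The late window opens 90 days after the last fraction, so the gap equals the elapsed treatment time.

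- Section 4.4.1 gives 39-41 fractions for chondrosarcoma and 40-44 for chordoma. The documents do not state fractions per week; five, on weekdays, is assumed.
- First to last fraction, over all starting weekdays: 39 fractions take 52-54 days, 40 take 53-55, 41 take 56, and 44 take 59-61.
- Section 4.6 says "Proton radiation therapy will in most instances be completed within 9 weeks of the start of treatment", which is 63 days and can be extended for breaks.
- The late window therefore opens at about day 142 (52 + 90) to day 153 (63 + 90) from start.

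**2. Effect of the gap on the rate.** Assume a constant hazard λ = −ln(1 − r)/5 with nominal 5-year risk r of 5%, 10% or 15%. The chance of onset in the gap is 1 − exp(−λd/365.25), with d = 52 to 63 days:

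- r = 5%: 0.15-0.18 points
- r = 10%: 0.30-0.36 points
- r = 15%: 0.46-0.56 points

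These are upper values. They count every onset in the gap, whereas 7.1.2.2 works by when an event is observed, so an event still present at the later boundary would be counted.

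**3. The plan's ±14%.** 1.96 × √(0.25/50) = 13.9%, so the figure is reproduced. It is the binomial half-width for 50 patients who are all fully observed.

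**4. A simple proportion against cumulative incidence.** Assumptions:

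- Accrual is uniform over 4 years and late toxicity starts at L = 90/365.25 = 0.246 years.
- Hazards are constant. The competing hazard is μ = −ln(p)/5 with p = 0.6 to 0.8, the 5-year range in 7.2.4. The plan describes that range as freedom from local failure, so it may understate progression or death.
- CIF(t) = exp(−μL) × λ/(λ+μ) × [1 − exp(−(λ+μ)(t − L))].
- The expected simple proportion is the mean of CIF(u) for u uniform on (c, c + 4), where c is the time from accrual close to the data cut.

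The earliest workable c is about 0.25 years, because the acute rate belongs to the same analysis and the last patient needs 90 days of follow-up. The latest is c = 1.

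Example, r = 10% and p = 0.8: λ = 0.0211, μ = 0.0446, and CIF(2) = 0.989 × 0.321 × 0.109 = 3.5%.

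| Nominal 5-year risk | Proportion, c = 0.25 | Proportion, c = 1 | CIF at 2 years | CIF at 5 years |
|---|---|---|---|---|
| 5% | 1.7-1.9% | 2.3-2.6% | 1.6-1.7% | 3.7-4.2% |
| 10% | 3.5-3.8% | 4.7-5.2% | 3.2-3.5% | 7.4-8.5% |
| 15% | 5.3-5.8% | 7.1-7.8% | 5.0-5.3% | 11.1-12.8% |

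The proportion rises by about one third between the two cuts, whichever nominal risk is used. At 10% that is 1.2-1.4 points, or 0.6-0.7 of a patient in 50. With p = 0.5 and 10% risk, the proportions are 3.3% and 4.4%, against 3.1% at 2 years and 6.8% at 5 years.

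**The case against.** **Scale.** The gap is worth a small fraction of one patient: 0.56% of 50 is 0.28. This stands. A reader might infer that severe events go unrecorded or that patient safety rules are weakened. The documents do not support that: toxicity is assessed throughout follow-up, and the stopping rules use the acute window only.

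**Two late definitions in Phase II.** A reader might infer that Phase II has two rival late boundaries. It does not. Section 7.1.4 belongs to the feasibility stage and describes tabulation of all toxicities, and Phase II inherits 7.1.2. The Phase II fault is a gap. Section 8.1 is too unclear to carry weight.

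**The estimator is not named.** Section 7.2.4 does not say simple proportion. That reading is inferred from the binomial ±14%, the absence of late toxicity from the Kaplan-Meier list, and the earlier analysis date. The objection stands as a limit on confidence; the missing time point and missing method are still missing.

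**The data cut.** A reader might take the cut to be the day accrual closes, and conclude that the proportion can rise by half (3.1-3.4% to 4.7-5.2% at 10% risk). That cut is not workable, because the last patients would lack the 90 days that the acute rate needs.

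**Five-year risk.** No section claims that the late rate estimates 5-year risk, and Phase II sets no late-toxicity threshold. The 5-year column shows only how far an undated rate can lie from a dated one.

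**Follow-up after progression.** Section 3.4.1 follows off-study subjects for toxicity, while 7.1.2.2 stops late-toxicity follow-up at progression. This might look like a contradiction, but general follow-up and an endpoint-specific rule can both stand.

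**Conclusion.** The boundary is wrong as written. Confidence is high because it rests on the text of 7.1.2.1, 3.4.1, 7.1.2.2 and 7.2.2. The gap is about 52-63 days, longer with breaks; its lower end depends on the assumed five fractions per week. Its effect is at most about 0.15-0.56 points for nominal 5-year risks of 5-15% under a constant hazard.

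The late-rate point is a cheap improvement, held with moderate confidence. The omission of a time point and of a method for unequal follow-up is plain. The size, a rise of about one third between cuts at 0.25 and 1 year, depends on reading the rate as a simple proportion and on assumed constant hazards and uniform accrual.

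**What to change.** **Boundary.** Make the windows contiguous and use one boundary in 7.1.2.2, 7.1.4 and 8.1. The simplest edit starts late toxicity in 7.1.2.2 more than 90 days from the start of therapy, which leaves the acute window and the stopping rules unchanged. The cost should be stated: late toxicity would then begin only 27-38 days after the last fraction (90 − 63 to 90 − 52) and would take in subacute events. Tabulate events between the two boundaries separately so that they stay visible. Extending the acute window instead would change what the stopping rules count.

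Classify by onset date, not visit date. Section 6.1 schedules an evaluation "at the inspection visit (approximately 90 days from treatment start"), and the 3-month post-treatment visit falls close to the later boundary.

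**Late rate.** In 7.2.4, report the cumulative incidence of first related Grade 3 or higher late toxicity with 95% intervals at named times: for example 1 and 2 years at the first analysis, and 5 years at the planned time-to-event analysis if enough patients remain at risk. Treat death, and progression where follow-up stops there, as competing events; Aalen-Johansen is one standard estimator. State the data cut and the numbers at risk. Say that ±14% assumes 50 fully observed patients and so applies to the acute rate.

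**Cost.** Wording edits and one standard analysis. Onset dates are needed, and the documents do not say whether they are recorded, so the case report form should be checked. Intervals widen somewhat: in simulation over nominal risks of 5-15%, the 2-year half-width is about ±3.6 to ±6.5 points with a cut at 1 year, against ±3.5 to ±6.1 if all 50 were followed to 2 years. At 5 years, with a cut 2 years after accrual, only about 6-10 of 50 remain at risk and the half-width is about ±6.3 to ±11.4 points.
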